22.2 Scientific Rationale for Study Design

The study design proposed is based on both preclinical and clinical data. Mcl-1 has been shown to be highly expressed in 2 human MCL cell lines and in tumours from 12 of 36 patients with MCL, and expression appeared to correlate with high-grade morphology ([Khoury et al 2003](#)). Aberrant expression of *MCL-1* has recently been implicated in lymphomagenesis ([Zhou et al 2001](#)), and it is hypothesised that the expression of *MCL-1* could contribute to the pathogenesis of MCL. [CCI](#) [REDACTED]

[REDACTED]

CCI

CCI

[figure not shown]
CCI

CCI

CCI

CCI

Clinical benefit in participants with MCL has also been reported for other CDK inhibitors. Partial response occurred in 11% (95% CI, 2%-28%) of participants with MCL receiving flavopiridol in a Phase II study, the median DoR was 3.3 months (range 2.8-13.2) (Kouroukis et al 2003). Among 16 participants with lymphoma receiving dinaciclib in a Phase I study, one participant had MCL and an 8% reduction in tumour mass was recorded (Baiocchi et al 2010).

Acalabrutinib, is approved by the FDA for the treatment of adults with MCL who have received at least one prior therapy. In a Phase II study of acalabrutinib involving 124 participants with r/r MCL, 81% of participants had a CR (40%) or PR (41%) after a median of 15.2 months of follow-up. Kaplan-Meier estimates of median DoR, PFS, and OS were not reached (Wang et al 2018). At long-term follow-up after a median of 38.1 months, the median DoR was 28.6 months (95% CI 17.5-39.1 months] and median PFS was 22.0 months (16.6-33.3 months) (Wang et al 2020).

The combination of AZD4573 and acalabrutinib may yield greater clinical benefit than either treatment alone. The effect of acalabrutinib in lowering the apoptotic threshold by induction of pro-apoptotic proteins or reduction of anti-apoptotic proteins (Deng 2017a) is expected to play an additive or synergistic role in targeting the apoptotic defects when administered in combination with AZD4573. CCI

As there are limited data available on AZD4573 monotherapy in patients with MCL, Part A of the Module 2 study design includes a window study of 2 cycles of AZD4573 monotherapy in each participant before starting combination treatment with acalabrutinib. This approach will allow AZD4573 monotherapy dose confirmation in participants with MCL before investigating the anti-cancer activity of the AZD4573 and acalabrutinib combination treatment.

For a monotherapy study using AZD4573 in MCL, participants with at least 2 prior lines of treatment including a BTK inhibitor would normally have been enrolled. Notably, the current study implements a window study design where the BTK inhibitor acalabrutinib will be subsequently added, as a combination treatment, to all participants who do not achieve a treatment response after 2 cycles of AZD4573 monotherapy. Hence, MCL participants who are BTK-inhibitor naive and have progressed after one prior line of treatment can be safely enrolled in the current window study, keeping in mind that they will receive appropriate BTK inhibition per protocol.

23 STUDY POPULATION – MODULE 2

Prospective approval of protocol deviations to recruitment and enrolment criteria, also known as protocol waivers or exemptions, is not permitted.

Participants must meet the inclusion and exclusion criteria of both the core and module protocol. Where there are differences in stringency or cut-off values, the specific module takes precedence. For example, if haematological medication parameters are stricter in the module than in the core, the Investigator should adhere to the module criteria.

23.1 Inclusion Criteria

Each participant should meet all the inclusion criteria (and none of the exclusion criteria) for this study in order to be assigned to a study cohort. Under no circumstances can there be exceptions to this rule.

NOTE: This Module will be enrolling participants with r/r MCL only.

For inclusion in the study, participants must fulfil all of the following criteria:

- 1 Participants must meet the eligibility criteria described in Section 5.1.
- 2 Participants with histologically confirmed r/r MCL for whom a clinical study is the best option (in the opinion of the investigator) for next treatment based on response and/or tolerability to prior lines of therapy.

PART A

- Participants with r/r MCL:
 - Diagnosis must be confirmed by biopsy and be immunohistologically characterised.
 - Tumour tissue must also be available for sending to AstraZeneca for pathology testing.

All participants in Part A must consent to and provide archival tumour specimens, preferably in the form of a formalin-fixed paraffin embedded block (tissue derived from the diagnostic tumour or a metastatic site). If this is not possible, an appropriate number of slides of freshly prepared unstained 5-micron sections from the archival tumour block may be provided as defined in the study Laboratory Manual. Archival tumour specimens must be obtained within 24 months before the first dose of IP. If archival material is unavailable or unsuitable for use, participants must consent to and undergo a fresh tumour biopsy during the screening period. A fresh biopsy is strongly encouraged and preferred, however, a participant will be enrolled based on the prior pathology report.

- 3 Presence of radiographically measurable lymphadenopathy or extranodal lymphoid malignancy (according to the Lugano criteria [[Cheson et al 2014](#)]).
- 4 Participants must have failed at least one prior therapy for the treatment of current disease and not be eligible for treatment with curative intent (e.g. allogeneic haematopoietic cell transplantation [HCT]). Eligible participants include both BTKi-naïve and BTKi-exposed.
- 5 Adequate haematologic function at Screening, as defined in [Table 27](#):
 - (a) No growth factor support within 14 days prior to the date of the screening laboratory assessment.
 - (b) No transfusions within 7 days prior to the date of the screening laboratory assessment.

Table 27 Criteria for Adequate Haematological Function

Category	Parameter	Value
Haematologic	Haemoglobin	≥ 8.0 g/dL
	Absolute neutrophil count	≥ 1000 cells/mm ³ (1.0 × 10 ⁹ /L)
	Platelet count	≥ 75,000 cells/mm ³ (75 × 10 ⁹ /L) without bone marrow involvement
		≥ 50,000 cells/mm ³ (50 × 10 ⁹ /L) with bone marrow involvement

- If indicated, transfusions or growth factors can be administered during the screening period, but such cases of deterioration of haematological function must be discussed with the Medical Monitor, to confirm start of study treatment.

- 6 **Optional** tumour biopsy on study: Participants are also encouraged to consent to and undergo an optional tumour biopsy at disease progression to support correlative biomarker studies.
- 7 All participants must be willing and able to provide mandatory baseline bone marrow biopsy/aspirate.

23.2 Exclusion Criteria

Participants are excluded from the study if any of the following criteria apply:

- 1 Participants must comply with the exclusion criteria described in Section [5.2](#).
- 2 Current refractory nausea and vomiting, malabsorption syndrome, disease significantly affecting gastrointestinal function, resection of the stomach, extensive small bowel resection that is likely to affect absorption, symptomatic inflammatory bowel disease,

partial or complete bowel obstruction, or gastric restrictions and bariatric surgery, such as gastric bypass.

- 3 Prior use of standard anti-lymphoma therapy or radiation therapy within 14 days of receiving the first dose of study treatment.
- 4 Requires or receiving anticoagulation with warfarin or equivalent vitamin K antagonists.
- 5 Requires treatment with strong CYP3A inhibitors or inducers (please refer to [Appendix F](#) for a list of strong inhibitors and inducers of CYP3A).
- 6 Requires treatment with proton-pump inhibitors (eg, omeprazole, esomeprazole, lansoprazole, dexlansoprazole, rabeprazole, or pantoprazole). Participants receiving proton-pump inhibitors who switch to H₂-receptor antagonists or antacids are eligible for enrolment to this study (see Section [24.8.4](#)).
- 7 Serologic status reflecting active hepatitis B or C infection:
 - (a) Participants who are anti-HBc positive and who are surface antigen negative will need to have a negative PCR result before enrolment. Those who are hepatitis B surface antigen positive or hepatitis B PCR positive will be excluded.
 - (b) Participants who are hepatitis C antibody positive will need to have a negative PCR result before enrolment. Those who are hepatitis C PCR positive will be excluded.
- 8 Active Cytomegalovirus (CMV) infection (positive CMV immunoglobulin M [IgM] and positive PCR result).
- 9 Requires or receiving therapeutic anticoagulants, with the exception of short-acting heparins, within 7 days of first dose of study treatment. Novel oral anticoagulants are allowed except for the initial high dose treatment period.
- 10 Participants on dual antiplatelet and therapeutic anticoagulant therapy (eg, aspirin and therapeutic doses of low molecular weight heparin).
- 11 History of or ongoing confirmed progressive multifocal leukoencephalopathy (PML).

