- e Vital signs (blood pressure, pulse rate, temperature) will be assessed after the participant has rested for at least 10 mins. Blood pressure and pulse rate will be measured at Screening, and on Day 1 of Cycle 1, Weeks 1-3 at the following timepoints: predose (within 2 h prior to infusion), 1 h after the start of the infusion (± 10 mins), at end of infusion (up to 10 mins post dose) and then 4 h (± 30 mins) and 6 h (± 30 mins) after start of infusion, from Cycle 1 Week 4 onwards, at predose (up to 30 mins prior to infusion), at the end of infusion (up to 30 mins post dose), and at the 30-day SFU. Temperature to be taken pre-infusion (up to 2 h prior to all infusions).
- f As the study is intended to recruit adults, height should only be measured at Screening. Weight to be measured at Screening, prior to infusion on Day 1 of each cycle, and at the 30-day SFU visit.
- g Participants should be in semi-supine position and resting for ≥ 10 mins before the ECGs. Single ECGs for local and central analysis are required at Screening and at the following timepoints: for Cycle 1, Weeks 1-5 and Cycle 2 Day 1 predose (at the day of infusion prior to infusion) and within 30 mins of the end of infusion; for Cycles 3+ on Day 1 within 30 mins after the end of infusion, and at the 30-day SFU visit.
- h All subjects will have CMV testing at Screening including serology testing for CMV immunoglobulin (Ig)G and CMV IgM and CMV DNA PCR testing
- i Cardiac troponin measurements are required at the following timepoints: Screening, Cycle 1, Weeks 1-5, predose (within 72 hours prior to infusion) and at 24 h after the start of the infusion, and Cycles 2+ on Day 1 of each cycle, predose (within 72 hours prior to infusion), and at the 30-day SFU visit. Note: either a troponin I or troponin T assay can be used per SoC at the respective hospital. If the hospital has both a SoC troponin I and troponin T assay available, the investigator shall use only one consistently for the duration of the study.
- j T4, cortisol, ACTH, and TSH to be taken at Screening, predose (within 72 hours prior to infusion) on Cycle 2, Day 1, and at the 30-day SFU.

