During the course of the study the Investigator will remain vigilant for increases in liver biochemistry. The Investigator is responsible for determining whether a participant meets PHL criteria at any point during the study. The Investigator participates, together with the

Sponsor, in review and assessment of these cases. Hy's Law (HL) criteria are met if there is no alternative explanation for the elevations in transaminases and total bilirubin levels.

If an unscheduled ECG is done at any time: troponin and an electrolyte panel* must be done to coincide with the ECG testing.

* can include: sodium, calcium, potassium, chloride, phosphate, magnesium.

If a participant is assessed as meeting PHL criteria, please refer to [Appendix E](#).

Hepatitis serology will be conducted at Screening. Hepatitis serology must include hepatitis B surface antigen (HbsAg), hepatitis B surface antibody (anti-HBs), anti-HBc, and hepatitis C (HCV) antibody. Participants who are anti-HBc positive, or have a known history of hepatitis B virus (HBV) infection, should be monitored every 3 months with a quantitative PCR test for HBV DNA (Section [17.1.10.4](#)). In addition, any participants testing positive for any hepatitis serology must have PCR testing for verification purposes.

Pregnancy: a sample for a pregnancy test will be collected from all female participants of childbearing potential at:

- Screening (serum)
- Cycle 1, Week 1:
 - Predose
- Cycles 2+: once every 21 days (\pm 7 days) prior to initiating a new cycle
- 30-day SFU

Pregnancy tests after Screening may be serum or urine. Urine β -hCG and quantitative serum β -hCG tests are permitted. If a urine β -hCG test is positive or indeterminate, quantitative serum β -hCG will be performed for confirmation. Additional testing may be performed at Investigator discretion for example in the event of suspected contraception failure.

CMV: All subjects will have CMV testing at Screening including serology testing for CMV immunoglobulin (Ig)G and CMV IgM and CMV DNA PCR testing. Subjects must have a negative result for CMV DNA PCR such that CMV DNA is not detected by PCR at Screening, to be eligible for the study. The Screening CMV serologies will be advisory only, to guide investigators in assessing the risk of new infection or reactivation of CMV while on study.

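### Module 2 exclusion criterion 8 does not exclude a CMV PCR-positive, IgM-negative participant whom Section 26.1.7 makes ineligible, and no stated rule ranks the two sections

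*Protocol*

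**What the plan says.** Two passages in the current Module 2 text set a CMV eligibility rule.

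- Section 23.2, exclusion criterion 8: "Active Cytomegalovirus (CMV) infection (positive CMV immunoglobulin M [IgM] and positive PCR result". The two results are joined by a conjunction.
- Section 26.1.7, CMV paragraph: "Subjects must have a negative result for CMV DNA PCR such that CMV DNA is not detected by PCR at Screening, to be eligible". The next sentence says "The Screening CMV serologies will be advisory only, to guide investigators in assessing the risk of new infection or reactivation of CMV while on study".

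Four other places bear on how a site would apply them.

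- Table 23, footnote h, has every participant tested: "All subjects will have CMV testing at Screening including serology testing for CMV immunoglobulin (Ig)G and CMV IgM and CMV DNA PCR testing". It sets no eligibility rule.
- Section 23.1 ties assignment to the criteria lists and allows no exceptions: "Each participant should meet all the inclusion criteria (and none of the exclusion criteria) for this study".
- Section 26.1.1 describes Screening as the step that confirms eligibility and refers to Sections 23.1 and 23.2. It does not refer to Section 26.1.7.
- The opening of Section 23 gives a precedence rule, "Where there are differences in stringency or cut-off values, the specific module takes precedence", in the context of differences between the core protocol and the module. It also rules out waivers of enrolment criteria.

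**The concern.** A site that works from the criteria list and a site that works from the laboratory section would reach different decisions about the same participant. The passages also disagree on what IgM is for. In criterion 8 a positive IgM is a necessary part of the exclusion; in Section 26.1.7 it has no bearing on eligibility.

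Since waivers are not allowed, the section a site followed decides whether such a participant counts as properly enrolled or as an eligibility deviation, with the procedures of Section 25.3 then possibly applying. Safety and tolerability are the primary objectives of Part A (Table 26). The protocol lists infection as an important potential risk for AZD4573 and an important identified risk for acalabrutinib (Section 26.1.10.7). The module plans about 12 participants (Section 27.2), so even one participant of uncertain eligibility would have to be explained in the report.

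**Working it through.** No sample size, power or error rate is involved, and the protocol states no figure to reproduce. The check compares the two rules over every combination of the two test results, with all other criteria taken as met.

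Inputs:
- Rule A (Section 23.2, criterion 8): excluded if IgM is positive and PCR is positive.
- Rule B (Section 26.1.7): ineligible if PCR is positive, whatever the IgM result.

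| IgM | PCR | Rule A | Rule B | Same outcome? |
|---|---|---|---|---|
| + | + | excluded | ineligible | yes |
| + | − | not excluded | not barred | yes |
| − | − | not excluded | not barred | yes |
| − | + | not excluded | ineligible | **no** |

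The rules differ in 1 of 4 combinations. That is a count of logical cases and says nothing about how often the discordant pattern occurs.

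Three further checks:

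1. *Can the pattern be seen?* Yes. Footnote h of Table 23 requires both IgM and PCR at Screening for every participant.
2. *Does another passage settle it?* Not in the text at hand. The precedence rule in Section 23 ranks module over core, and both passages here belong to Module 2. Sections 23.1 and 26.1.1 direct sites to the lists, and neither Module 2 list contains the PCR-negative requirement.
3. *Could the conjunction be read as loose wording?* Criterion 7, directly above, excludes participants who are PCR positive for hepatitis B or C with no further condition. Next to it, a reader would reasonably take the conjunction in criterion 8 as deliberate.

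**The case against.** The strongest reply is that the rules can be applied together. Criterion 8 says who is excluded; it does not declare everyone else eligible. Section 26.1.7 adds a further necessary condition. A site that applies the whole protocol would not enrol a PCR-positive, IgM-negative participant and would breach nothing in Section 23.2 by declining. This stands in part. A reader might infer that the protocol makes the same person both eligible and ineligible, and the text does not go that far: it does not issue two commands that cannot both be obeyed. What remains is that the list to which sites are directed omits a condition stated elsewhere. On the cumulative reading, the IgM element of criterion 8 would also have no effect.

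A second reply is that core Sections 5.1 and 5.2, which the module criteria import, are in the part of the protocol not available for this check. A core CMV criterion could decide the outcome for the disputed participant. It would not make the two Module 2 passages agree.

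A third reply concerns consequences, and most of it stands. Table 43 puts everyone who received any treatment in the Safety and Full Analysis sets, and Section 24.3 counts anyone dosed as evaluable. Only the pharmacokinetic set refers to protocol deviations, and only those that may affect pharmacokinetics. Baseline CMV status is to be recorded under either rule. No hypotheses are tested (Section 27.1).

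Finally, Section 18.5 records a permanent halt to enrolment, and Section 22 opens Module 2 only once the Module 1 combination dose is established. The available text does not show that anyone entered Module 2.

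**Conclusion.** The inconsistency is real and lies in current, unredacted text. Criterion 8 does not exclude a PCR-positive, IgM-negative participant, Section 26.1.7 makes that participant ineligible, and nothing in the available text ranks the two sections. It deserves correction because it concerns eligibility in a module whose primary objective is safety, and because the criteria list is where sites are told to look.

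Its size is small and cannot be given as a number. The protocol does not say how often the discordant pattern occurs, and it may be zero. A reader might scale it as one or two of about 12 participants (1/12 = 8%, 2/12 = 17%), but nothing in the document supports those counts. Nor does it support an inference that the primary safety analysis would change, because that set includes all dosed participants, or that there are enrolled participants to reclassify, because Module 2 enrolment is not shown.

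The conclusion assumes that the unseen core criteria do not settle the matter. If they bar PCR-positive participants, the practical outcome would be clear, but the two Module 2 passages would still need aligning.

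**What to change.** Reconcile exclusion criterion 8 in Section 23.2 with the CMV paragraph of Section 26.1.7 so that one eligibility rule stands and IgM has the same role in both. This review takes no view on which rule should stand.

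Check the Module 2 screening results. If any participant was enrolled with a positive CMV PCR and a negative IgM, list that participant and classify eligibility under the reconciled rule. If there is none, or if nobody entered Module 2, say so and take it no further.

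The cost is about one sentence of protocol text and a look at screening tests that the protocol already requires. No analysis changes. With enrolment halted, the prospective benefit is limited; the remaining value lies in consistent deviation reporting and in having a single rule on record.

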23.3 Lifestyle Considerations

Please refer to Section [5.3](#), in addition to Section [23.3.1](#).

23.3.1 Meals and Dietary Restrictions – Module 2

Acalabrutinib is best taken with water and can be taken with or without food. As acalabrutinib is metabolised by CYP3A, participants should be strongly cautioned against using herbal remedies or dietary supplements (in particular, St John's wort, which is a potent CYP3A inducer).

Otherwise, participants should maintain their regular diet unless modifications are required to manage an AE such as diarrhoea, nausea, or vomiting.

23.4 Screen Failures

Please refer to Section [5.4](#).

23.5 Justification for Dose

Part A

The ongoing FTIH study (D8230C00001) has demonstrated that administration of AZD4573 is tolerated in participants with r/r haematological malignancies. The study has established a recommended Phase II dose (RP2D) of AZD4573 monotherapy in DLBCL participants involving intra-patient dose ramp up in Cycle 1 from a starting dose on Day 1 (6 mg), with subsequent titration to the intermediate dose on Day 8 (9 mg), and to the target dose of 12 mg on Day 15, with weekly IV administration thereafter at the target dose (data on file, AstraZeneca). This established dose of AZD4573 monotherapy in DLBCL participants will be administered in Part A, Period 1 of Module 2 to participants with r/r MCL.

Acalabrutinib 100 mg BID is the approved dosage for patients with MCL ([Calquence United States Prescribing Information](#)). Module 1 of this study evaluates the safety and tolerability of AZD4573 in combination with acalabrutinib 100 mg BID in participants with DLBCL. The target dose of AZD4573 9 mg was tolerated in combination with acalabrutinib, and the target dose level of 12 mg is being explored in participants with DLBCL (data on file, AstraZeneca).

The dose of AZD4573 administered in combination with acalabrutinib during the combination Period 2 of Module 2 to participants with MCL will be established based on emerging data from Module 1 and will be a dose deemed by the SRC to be tolerated in combination with acalabrutinib in participants with DLBCL (ie, the RP2D in DLBCL).

23.6 End of Study Definition

Please refer to Section [4.5](#) for the definition of the end of the study. The end of Module 2 is defined as the last scheduled visit or contact of the last participant enrolled in this Module. In addition, the study may be terminated, or individual centres closed at the discretion of AstraZeneca (please refer to [Appendix A 9](#)). AstraZeneca may also terminate the module prematurely if concerns for safety arise within this study or in any other study with AZD4573 and/or acalabrutinib.

The data cut-off for the primary analysis will occur approximately 6 months following last-participant first-dose or when 75% of participants have progressed or died in Part A, whichever occurs first.

Any patients still receiving study intervention at the completion of the primary analysis will be able to continue to receive the intervention if still considered to be deriving clinical benefit.

Such patients will continue to be monitored for all SAEs up to 30 days after the last dose of the intervention therapy. Participants may be eligible to enrol in either a future rollover study of AZD4573 monotherapy or a future rollover study of the combination of AZD4573 and other anti-cancer agents, respectively.

The results from Module 2 will be reported to Regulatory Authorities within one year of the end of module.

24 STUDY INTERVENTION – MODULE 2

Study intervention is defined as any investigational intervention(s), marketed product(s), placebo, or medical device(s) intended to be administered to a study participant according to the study protocol.

